9.7.3.4.4 Assessing effect modification

Estimation of effect modification of the adjusted hazard ratios will be conducted for secondary objectives 28-31 in Section 8.2.

The crude and adjusted hazard ratios will be estimated as described in Sections 9.7.1.3.1 and 9.7.1.3.3 within each level of the potential modifier. Cohort(s) of interest for each objective are indicated by “X” in Table 11.

Table 11. Study cohorts relevant to effect modification objectives

Objective number	Brief description	Complete study population	Breastfeeding status available	IUD type available
Uterine perforation outcome				
28	Breastfeeding modifies early (≤ 14 weeks) vs. late (> 14 weeks) postpartum and vice versa		X	
29	IUD type modifies breastfeeding		X	
31	IUD type modifies postpartum categories			X
30	IUD type modifies breastfeeding		X	
32	IUD type modifies postpartum categories			X

IUD = intrauterine device.

For objective 28, the Cox models will include breastfeeding status, early (≤ 14 weeks) versus late (> 14 weeks) postpartum, and their interaction. The *P* value of the type 3 group test for interaction will be reported. For reporting purposes, the group of no breastfeeding and > 14 weeks postpartum will be considered the referent, and hazard ratios will be reported for postpartum period ≤ 14 weeks and breastfeeding, ≤ 14 weeks and no breastfeeding, and > 14 weeks and breastfeeding. The adjusted hazard ratio will be obtained using the weighted Cox model (Section 9.7.1.3.3). One propensity score model (using these four categories) will be developed. Balance on baseline covariates among the four categories in the weighted sample will be assessed.

For objectives 29-32, the Cox models will include the exposure of interest (breastfeeding status or postpartum categories), the outcome of interest (uterine perforation or IUD expulsion), IUD type, and the interaction between exposure and IUD type. The *P* value of the type 3 group test for interaction will be reported. The hazard ratio for exposure of interest will be reported within each level of the IUD type. The adjusted hazard ratio will be obtained using the weighted Cox model (Section 9.7.1.3.3). The weights will be estimated using the same propensity score models developed for the exposure-outcome pairing (Table 6).

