4.1.5 Confounder or Bias Adjusted Analyses

Confounding will be controlled through the use of propensity scores, based on the values of covariates at the time of IUD insertion. The propensity score estimates the probability that a given patient will be exposed conditional on measured covariates and can serve as a summary confounder variable. Propensity scores can perform better than conventional regression methods when the number of events relative to the number of potential confounders is small, because rather than having to model the events with many variables, which may lead to overfitting of the outcome model, one can instead model the exposure, for which the larger number of exposed people provides sufficient data to accommodate a rich model (Cepeda et al., 2003). This advantage may be important in this study, given the low number of expected events, particularly for uterine perforation, within this study.

The steps in estimating adjusted exposure effects are listed as follows:

1. Derive variables that will be considered for inclusion in the propensity score models.
2. Assess balance between exposure groups in the sample.
3. Identify key variables to be included in the propensity score model.
4. Estimate propensity scores and assess the overlapping area among all exposure groups.
5. Calculate weights, normalize the weights, and examine the normalized weights.
6. Assess balance between exposure groups in the weighted sample.
7. Add to the propensity score model additional terms (e.g., interaction or higher order terms) of the covariates that do not balance.
8. Fit the new propensity score model and estimate the propensity scores.
9. Repeat steps 5-8 until all the key covariates are balanced.
10. Estimate the exposure effect that accounted for the confounders via weighting.

Propensity scores for exposure variables will be estimated by fitting a logistic regression model (for dichotomous exposure variables) or a multinomial logistic regression model (for exposure variables with more than two categories). The dependent variable in the propensity score model is exposure status (e.g., women breastfeeding at the time of IUD insertion vs. not breastfeeding at the time of IUD insertion).

Breastfeeding status, postpartum timing, and IUD type will be included within the propensity score model (as independent variables when not the dependent variable). Other covariates will be assessed

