The balance across exposure groups will be assessed before and after weighting. The distribution of each variable will be compared between categories of the exposure variable, and balance parameters (i.e., standardized differences) (Austin and Stuart, 2015) will be calculated. Pairwise balance parameters (e.g., pairwise standardized differences) will be used for the categorical exposure variable in which each category will be compared to the referent group (> 52 weeks postpartum for postpartum period). The maximum of the pairwise standardized differences will also be reported. The balance between exposure groups will be assessed overall and within each data source. If the groups are unbalanced on key covariates after application of overlap weighting, then the logistic regression model will be revised by including interaction terms (e.g., with data source), higher order terms, or transformation of variables, and the covariate balance between the groups overall and within each data source will be re-evaluated based on the revised model. When satisfactory balance between the exposed and unexposed groups is achieved, the weighting will be incorporated in modeling for confounder-adjusted outcome assessments (Section 4.1.5). The exposure groups are considered balanced if the standardized difference is less than 0.20 (generally considered small) (McCaffrey et al., 2013). If satisfactory balance is difficult to achieve, which is not expected for overlap weighting, matching of patients between groups may be considered.

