6.2.2.5 Assessing Effect Modification

Estimation of effect modification of the adjusted hazard ratios will be conducted for secondary objectives 28, 29, 31. The crude and adjusted hazard ratios will be estimated as described in Sections 4.1.4 and 4.1.6 within each level of the potential effect modifier. Due to the expected sparse outcomes and the data source restriction on IUD type, these analysis will be conducted only using the pooled data, not by data source.

For objective 28, the Cox model will include breastfeeding status, early (≤ 14 weeks) versus late (> 14 weeks) postpartum status, and their interaction. The P value of the type 3 group test for interaction will be reported. The hazard ratio for breastfeeding status (yes vs. no) will be reported within each level of early (≤ 14 weeks) and late (> 14 weeks) postpartum status. The hazard ratio for postpartum status (≤ 14 weeks vs. > 14 weeks) will be reported within each level of breastfeeding status. In addition, for reporting purposes, the group of no breastfeeding and > 14 weeks postpartum will be considered the referent, and hazard ratios will be reported for postpartum period ≤ 14 weeks and breastfeeding, ≤ 14 weeks and no breastfeeding, and > 14 weeks and breastfeeding. The adjusted hazard ratio will be obtained using the weighted Cox model. One propensity score model using these four (2×2) categories as the dependent variable will be developed. Balance on baseline covariates among the four categories in the weighted sample will be assessed.

For objectives 29 and 31, the Cox models will include the exposure of interest (breastfeeding status or postpartum categories), IUD type, and the interaction between exposure and IUD type. The P value of the type 3 group test for interaction will be reported. The hazard ratio for the exposure of interest will be reported within each level of IUD type. The adjusted hazard ratio will be obtained using the weighted Cox model. The weights will be estimated using the same propensity score models developed for the exposure-outcome pairing (Section 9.3).

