Objectives 20 through 27^{c,d}	Comparative analysis for IUD expulsion		Same set of tables and figures as objectives 1, 2, 14-19, excluding Tables 1.4 and 2.4 (106 tables + 47 figures)
Objective 28	Effect modification		
Table 28.1	Effect modification of breastfeeding status and postpartum status on uterine perforation	Layout 11	Pooled (1 table)
Objective 29	Effect modification		
Table 29.1	Effect modification of IUD type on breast feeding status and uterine perforation	Layout 12.1	Pooled (1 table)
Objective 30	Effect modification		
Table 30.1	Effect modification of IUD type on breast feeding status and IUD expulsion	Layout 12.1	Pooled (1 table)
Objective 31	Effect modification		
Table 31.1	Effect modification of IUD type on postpartum status and uterine perforation	Layout 12.2	Pooled (1 table)
Objective 32	Effect modification		
Table 32.1	Effect modification of IUD type on postpartum status and IUD expulsion	Layout 12.2	Pooled (1 table)
Development of propensity score models			
Tables 33.1.1 through 33.1.2	Assessing relationship with outcome: crude HR for baseline covariates	Layout 4	Pooled (2 tables)
Tables 33.2.1 through 33.2.9	Assessing confounding effect: HR adjusted for one covariate	Layout 5	Pooled (9 tables)
Tables 33.3.1 through 33.3.15	Propensity score model	Layout 6	Pooled (15 tables)
Figure 33.1.1 through 33.1.15	Histograms with kernel smoothing of propensity scores by exposure		Pooled (15 figures)
Impact of transition from ICD-9-CM to ICD-10-CM			
Tables 34.1	Percentage of uterine perforation or IUD expulsion prior to and after implementation of ICD-10-CM coding	Layout 13	Pooled and by site (1 table)

HR = hazard ratio; ICD-9-CM = *International Classification of Diseases, 9th Revision, Clinical Modification*; ICD-10,CM = *International Classification of Diseases, 10th Revision, Clinical Modification*; IUD = intrauterine device.

Note: In the report, analysis tables related to IUD type will report only the results across all sites, not by site. However, by-site analyses may be conducted for internal purposes and will not be shared with Bayer.

^a Table layouts are included in Section 9.5.

- ^b If breastfeeding status, postpartum timing, or IUD type are not included within a propensity score (as independent variables when not the dependent variable), then a separate Cox model also including these variables as covariates will be developed. If this occurs additional tables will be added using Table Layout 7.

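### Objectives 29-32 report hazard ratios within each IUD type, but no balance check within type is planned, so residual confounding could pass for effect modification

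*SAP*

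**What the plan says.** For objectives 29 and 31, SAP 6.2.2.5 fits a weighted Cox model with the exposure, IUD type and their interaction. It reports the exposure HR within each IUD type and a type 3 interaction P value. On the weights it says: "The weights will be estimated using the same propensity score models developed for the exposure-outcome pairing". SAP 6.3.1 carries the approach to expulsion (objectives 30 and 32), and Protocol 9.7.3.4.4 gives the same rule for all four. In the SAP 9.3 model list, objectives 29 to 32 use models 1, 5, 2 and 6 respectively; models 1 and 2 also serve the primary objectives.

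SAP 4.1.5 sets the rules on balance:
- "Breastfeeding status, postpartum timing, and IUD type will be included within the propensity score model (as independent variables when not the dependent variable".
- "The balance between exposure groups will be assessed overall and within each data source".
- "The exposure groups are considered balanced if the standardized difference is less than 0.20". Protocol 9.7.1.3.2 gives 0.1 as its example.
- The repair step is: "Add to the propensity score model additional terms (e.g., interaction or higher order terms) of the covariates that do not balance".

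In SAP 9.4 the only output for objective 29 is one pooled HR table ("Effect modification of IUD type on breast feeding status and uterine perforation"). Objectives 30-32 likewise have one table each, with no balance table or figure. Objective 28, in the same SAP section, has its own four-category propensity model, and: "Balance on baseline covariates among the four categories in the weighted sample will be assessed".

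**The concern.** An HR reported within copper users is adjusted only if the exposure groups are comparable among copper users. A propensity model with IUD type as a main effect does not secure that. For a two-level exposure, overlap weights from a logistic model equalize the weighted means of the terms in the model, over the sample on which it was fitted. With IUD type as a term, the proportion using copper is equal across exposure groups. With a covariate as a term, its mean is equal overall. Neither equalizes the covariate within copper or within LNG unless the covariate-by-type product is also a term.

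Opposite imbalances in the two types can therefore cancel in the overall table. The repair step responds to imbalance overall or by data source, so it need never act on this. Copper carries about a fifth of the sample, so a small imbalance in LNG offsets a larger one in copper. What is left would show as a difference between the two stratum HRs, which is exactly what objectives 29-32 report. The footnote to the Table 5 discussion in Protocol 9.5 records that FDA asked for enough users of both types to compare them by early insertion and breastfeeding status.

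**Working it through.** **Inputs from Protocol 9.5.** 60,000 women with known breastfeeding status; 60:40 breastfeeding; 80:20 LNG to copper; 1.3 perforations per 1,000 insertions; 225,000 first insertions split 5:20:5:70 by postpartum category; two-sided alpha 0.05; Schoenfeld formula.

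**Reproducing a planning figure.** Table 5 gives 47% power for LNG versus copper among 36,000 breastfeeding women at HR 2.0. Events = 36,000 x 0.0013 = 46.8. Power = Phi(sqrt(46.8 x 0.8 x 0.2) x ln 2 - 1.96) = Phi(1.897 - 1.96) = 47.5%. The inputs are read correctly.

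**Illustration of the mechanism.** The documents give no covariate-by-device figures, so these are assumptions: one binary covariate X with 30% prevalence in both types, 20% copper, 60% exposed, a common intercept, and an X-exposure odds ratio of 2 in LNG and 1 in copper. This is an exact population calculation for a two-level exposure.

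1. True exposure probabilities: 0.562 for X = 0 in both types and for X = 1 in copper; 0.720 for X = 1 in LNG. Check: 0.7 x 0.562 + 0.3 x (0.8 x 0.720 + 0.2 x 0.562) = 0.60.
2. The logistic model with main effects of X and IUD type fits 0.572 and 0.697 in LNG (X = 0, 1), and 0.523 and 0.654 in copper.
3. Overlap weights are 1 - e for exposed and e for unexposed. Weighted prevalence of X in copper:
   - exposed: 0.3 x 0.562 x 0.346 / (0.3 x 0.562 x 0.346 + 0.7 x 0.562 x 0.477) = 0.237
   - unexposed: 0.3 x 0.438 x 0.654 / (0.3 x 0.438 x 0.654 + 0.7 x 0.438 x 0.523) = 0.349
4. Standardized difference in copper = (0.237 - 0.349) / sqrt((0.237 x 0.763 + 0.349 x 0.651) / 2) = -0.25. In LNG the prevalences are 0.280 and 0.251, giving +0.07. Overall both are 0.271, giving 0.000.
5. With no true exposure effect and covariate HR h, the apparent stratum HR is about (1 + p1(h - 1)) / (1 + p0(h - 1)), where p1 and p0 are the weighted prevalences of X in exposed and unexposed. For h = 2: copper 0.917, LNG 1.023, ratio 0.90. For h = 3: copper 0.869, LNG 1.039, ratio 0.84.

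Other assumed odds ratios, same method:

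| OR in LNG, copper | SMD overall | SMD in LNG | SMD in copper | Spurious copper/LNG ratio (h = 2, 3) |
|---|---|---|---|---|
| 2, 2 | 0.000 | 0.00 | 0.00 | 1.00, 1.00 |
| 1.5, 1 | 0.000 | +0.04 | -0.15 | 0.94, 0.90 |
| 2, 1 | 0.000 | +0.07 | -0.25 | 0.90, 0.84 |
| 2, 0.5 | 0.000 | +0.14 | -0.50 | 0.80, 0.70 |

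Adding the X-by-type term, or fitting within type, gives 0.000 in both types and a ratio of 1.00 in every row.

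**Scale against sampling error (objective 29).** Expected perforations = 60,000 x 0.0013 = 78: 62.4 in LNG and 15.6 in copper. SE of the log ratio of HRs = sqrt(1/(62.4 x 0.24) + 1/(15.6 x 0.24)) = 0.58. The ratio detectable with 80% power is exp(0.578 x 2.80), about 5.0. A spurious ratio of 0.90 or 0.84 is 0.18 or 0.30 SE and moves the rejection rate of a 5% test to about 5.4% or 6.0%.

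**Copper counts for objective 31.** In each of the <=6-week and >14-to-<=52-week groups, 11,250 x 0.2 = 2,250 women, with about 2.9 perforations.

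**The case against.** Much of the case for leaving the plan alone stands.

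- *No evidence that the relations differ by device.* The bias needs covariate-exposure relations that differ between LNG and copper users, or a needed term missing from the model. The documents give no sign of either. With odds ratios of 1.5 and 1, the copper imbalance of 0.15 also passes the SAP limit, though not the protocol's example of 0.1.
- *IUD type is already in the model.* SAP v2.0 added it deliberately, and interaction terms are allowed where balance fails. This mitigates the problem but does not close it, because the trigger never looks inside device type.
- *Imprecision dominates for perforation.* On the planning inputs this is right. It does not remove the gap: sampling error shows in the interval, while this bias shows in no planned table. No expulsion rate is given, so the same cannot be said of objectives 30 and 32.
- *These are secondary objectives.* The interaction P value is reported without a decision rule.

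A reader might infer from objective 28 that the plan contradicts itself by treating IUD type differently. The documents do not support that. Objective 28 compares both factors and sets three cells against a common referent, so it needs four-cell balance. In objectives 29-32 IUD type is only the modifier, and a different model is legitimate. What is missing is the within-type balance check.

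**Conclusion.** The gap is real and cheap to close. Stratum HRs are planned for objectives 29-32 with weights whose balance is never examined in those strata, so copper can breach the SAP's 0.20 limit unseen. The possible size runs from nothing (equal relations) to a spurious ratio of HRs of 0.90 or 0.84 under odds ratios of 2 and 1, and further under stronger differences. All non-zero figures rest on an assumed covariate.

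A reader might infer that the copper results will be confounded by some predictable percentage, or that the primary findings are in doubt. Neither follows. The documents contain no covariate-by-device data, and the primary HRs are not reported by device. The calculation covers a two-level exposure (objectives 29 and 30). For the four postpartum categories the same lack of a within-type check applies, but no size was computed.

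One further point bears on the fix. SAP 5.1.1 allows unknown IUD type to be a separate group when the propensity model is developed, while Table Layouts 12.1 and 12.2 show only LNG and copper. If the weights come from the wider sample, even exact overall balance need not hold among the women analysed.

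**What to change.** Add to SAP 6.2.2.5 and 6.3.1, for objectives 29-32:

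1. Compute the weights on insertions with known IUD type.
2. Tabulate weighted standardized differences by exposure within LNG and within copper, from pooled data only, since IUD type is not reported by data source. For postpartum timing, compare each category with >52 weeks, as SAP 4.1.5 already does. List these tables in SAP 9.4.
3. Where a difference exceeds the SAP limit, add covariate-by-IUD-type terms to the propensity model, or fit it within type, and re-check before reporting the stratum HRs.

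Keep these refits separate from models 1 and 2 so that the primary weights do not change. Type-specific models should not be the default: with about 2,250 copper women in each of the two smallest postpartum groups, fully interacted fits could be unstable.

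The cost is a few extra tables and refits on existing data, and slightly noisier weights in the copper stratum where terms are added.

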6.3 Analysis of Secondary Variable(s)

6.3.1 Analysis of IUD Expulsion

The secondary endpoint in the study is time to diagnosis of IUD expulsion (defined in Table 1). In the following groups of women, the adjusted hazard ratios for IUD expulsion will be evaluated:

- Objective 20. Women who were breastfeeding at the time of the first observed IUD insertion versus those who were not breastfeeding at the time of the first observed IUD insertion.
- Objective 23. Women who had a first observed IUD insertion within different time periods postpartum (i.e., ≤ 6 weeks, > 6 weeks and ≤ 14 weeks, > 14 weeks and ≤ 52 weeks) versus those who had a first observed IUD insertion late in the postpartum period (more than 52 weeks postpartum, including those without recorded delivery in the previous 52 weeks).

Study objectives related to IUD expulsion and the corresponding exposures and analysis sets are summarized in Section 9.2. Analyses will be the same as those for uterine preformation, as described

in Section 6.2, except (1) no sensitivity analyses will be conducted and (2) assessment of effect modification using a Cox model including breastfeeding status, early (≤ 14 weeks) versus late (> 14 weeks) postpartum status, and their interaction will not be conducted.

6.3.2 Analysis of Difficult Insertion

The prevalence of indicators of a difficult insertion (objective 13) will be presented via contingency tables including frequencies and percentages of each level of each exposure and outcome variable for five individual indicators of difficult IUD insertion—cervical dilation, ultrasound guidance, paracervical block, provider note, use of misoprostol—plus an indicator for *any* difficult insertion. Analyses will be conducted for the first observed IUD insertion using the pooled data and by data source (Analysis Tables 13.1-13.5). In addition, difficult insertion indicators will be included in summary tables of baseline characteristics.

6.3.3 Impact of Transition From ICD-9-CM to ICD-10-CM²

The results of this study are dependent on accurate capture of data from source files based on definitions of variables in this study. Since variables will be determined from diagnosis codes (ICD-9-CM, ICD-10-CM), Current Procedural Terminology codes, medication codes (National Drug Codes), and clinical notes (e.g., via natural language processing software) there is a possibility of misclassification. Algorithms for the outcome variables (uterine perforation and IUD expulsion) have been validated in these four databases prior to use of ICD-10-CM coding. No formal validation of the algorithms with ICD-10-CM codes to identify uterine perforation or IUD expulsion will be performed. However, the rate of these outcomes will be reviewed before and after implementation of ICD-10-CM coding to ensure consistency over time. Specifically, 01 October 2015 is the date of transition from ICD-9-CM to ICD-10-CM. The “before” time period will be defined as 01 October 2014 through 30 September 2015, and the “after” time period will be defined as 01 October 2015 through 30 September 2016. The number of patients with an outcome in each time period and the number of patients enrolled in each time period will be reported by data source research partners. The percentage of patients with an outcome among enrolled patients in each time period will be calculated. This analysis will be conducted using the “complete study population” defined in Section 5.1. The count and percentage will be reported for each outcome before and after the transition in the pooled data and by data source (planned Analysis Table 34.1).

